8.2 Handling of Dropouts, Missing Data

The distribution of subjects excluded from FAS/PPS will be described by vaccine group.

For immunogenicity data, it may be reasonable to consider missing immunogenicity values as missing completely at random (MCAR), i.e., not informative. Therefore, the immunogenicity analysis will comprise a complete case analysis only, without introducing any bias. Additional

sensitivity analysis will be considered if the percentage of subjects with missing data is more than 10%.

Solicited AEs are collected using eDiary from Day 1 to Day 7 post-vaccination. If a solicited local or systemic AE continues beyond day 7 after vaccination, recording in the Subject eDiary will be continued until the event(s) resolved or for a maximum of 14 days after vaccination. If the data have not been recorded for all 7 days, the assessment is considered missing and excluded from analysis. In case at least one day is filled in but other days are missing the presence or absence of the event will be based on the available data

8.3 Multicenter Studies

There will be no adjustment for multiple centers.

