3.10 End of Study

Most clinical trials intended to support the efficacy and safety of an Investigational Product proceed to full completion of planned sample size accrual.

Evaluation of the primary and secondary immunogenicity objectives requires the testing of biological samples from the study subjects, which can only be completed after all of the samples for these objectives are collected. The last samples for the analysis of the secondary objectives will be taken at Visit 5 (Day 181). The last clinical assessment for the secondary safety objective will be at Visit 6 (Day 271). Accordingly, for the purpose of this protocol, end of study is defined as the completion of the testing of the Visit 5 (Day 181) biological samples, to be achieved no later than 8 months after collection of the last biological sample at Visit 5 (Day 181), or the Last Subject Last Visit, whichever is later. The local end of the study is defined as the Last Subject Last Visit within the country.

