6.6 Vaccine Supply, Labeling, Storage and Tracking

The Sponsor will ensure the following:

- Supply the study vaccines.
- Appropriate labeling of all study vaccines provided that it complies with the legal requirements of each country where the study is to be performed.
- Appropriate storage and distribution of study vaccines.

The investigator must ensure the following:

- Acknowledge receipt of the study vaccines by a designated staff member at the site, including:
- Confirmation that the vaccines were received in good condition and in the right amount;
- Confirmation that the required temperature range during shipment from the Sponsor to the investigator's designated storage location has been maintained;

Protocol Number: V118_23

Product Name: aQIV

Document Status: Final Version 3.0, Document Date: 11 Jul 2022

- Report any temperature deviation and do not use vaccines until further confirmation by the Sponsor or delegate that the vaccines are authorized for use.
- Proper storage of the study vaccines, including:
 - Storage in a secure, locked, temperature-controlled location;
 - Proper storage according to the instructions specified on the labels and in the Investigator Pharmacy Manual;
 - Appropriate record keeping and inventory of the study vaccines, including regular documentation of adequate storage temperature.
 - Appropriate use of the study vaccines, including:
 - Use only in accordance with the approved protocol.
 - Proper handling, including confirmation that the vaccine has not expired or been subject to a temperature excursion prior to administration.
 - Appropriate documentation of administration of vaccines to study subjects including:
 - Date, dosage, batch/lot numbers, expiration dates, unique identifying numbers assigned to subjects and study vaccines, and time of vaccine administration. This information will be maintained in an accountability log that will be reviewed by the site monitor;
 - Reconciliation of all vaccines received from the Sponsor. Reconciliation is defined as maintaining records of which and how many vaccines were received, which vaccines were administered to subjects, which vaccines were destroyed at the site, and which vaccines were returned to the Sponsor, as applicable.
 - Proper adherence to the local institutional policy with respect to destruction of study vaccines;
 - Complete record keeping of vaccine use, wastage, return or destruction, including documentation of:

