8.4.2.3.3 Statistical Methods

All statistical analyses for HI (or MN if applicable) titers will be performed on the logarithmically (base 10) transformed values. Individual HI titers below the detection limit (<10) will be set to half of that limit (5); values above the upper limit of quantification will be set to the upper limit.

Reverse cumulative distribution curves will be derived by time-point and strain.

Crude estimates for GMTs, GMFIs, and pertaining 2-sided 95% CIs will be calculated assuming a log-normal distribution of the titers and will be completed by providing minimum, maximum and median titers for each treatment group. Binary data (i.e., percentages of subjects with seroconversion and with titer $\geq 1:40$) will be summarized for each group using crude estimates and will be reported together with 2-sided 95% CIs calculated according to Clopper's and Pearson's method ([Clopper and Pearson 1934](#)). No multiplicity adjustment to the CI levels will be implemented.

The analysis model for the HI GMT will use a general linear model on log-transformed (base 10) Day 22 titers as the outcome variable and as covariates: treatment groups (aQIV, and QIV), prevaccination titer (\log_{10} transformed), age stratum, gender, and history of any influenza vaccination within the 3 previous influenza seasons. From this model, adjusted differences in the least square means (on the \log_{10} scale) will be produced with 95% confidence limits for QIV versus aQIV. The estimated difference and the confidence limits will be back-transformed to obtain *adjusted GMT ratios* with 95% confidence limits. The adjusted GMT ratio will be the result for which the assessment of the HI GMT primary endpoint will be based on. Each of the 4 strains will be analyzed separately.

Potential covariate interaction effects will also be examined in the fit of the GLM, as well as the other co-variates such as age taken as a continuous factor.

The differences of binary endpoints (i.e. seroconversion or titer $\geq 1:40$) will be compared using the Miettinen and Nurminen method ([Miettinen and Nurminen 1985](#)). Additional supportive analyses might be done using generalized linear models with factors for treatment group, age subgroup, prevaccination titer (\log_{10} transformed) as well as vaccination history. Adjusted differences between treatment groups with 2-sided 95% CI will be calculated based on the model and potential interaction effects will be examined.

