8.1 Adjustment for Covariates

The main statistical analysis includes descriptive statistics for the overall population. Subgroup analyses will be done by age cohort (50-59 and 60-64 year of age), previous vaccination history, sex, race, ethnicity, and comorbidity risk scores (Hak score, <50 and ≥ 50). Summary tables will show unadjusted GMTs for each vaccine group by time point.

Adjusted GMTs will be calculated based on the \log_{10} -transformed antibody titers at Day 22/181/271 using an ANCOVA model which includes the vaccine group (aQIV and QIV), \log_{10} -transformed pre-vaccination antibody titer, age cohort (50-59 or 60-64 year of age), sex, and history of any influenza vaccination within the 3 previous seasons (yes/no). The main analysis of binary immunogenicity endpoints (i.e., percentages of subjects with seroconversion) will not be adjusted for any of the covariates. Binary data will be summarized for each group using unadjusted estimates and will be reported together with two-sided 95% CIs calculated according to the Clopper-Pearson method. Sensitivity analysis may be done to include the vaccine group (aQIV and QIV), stratification factors age and previous vaccination history, and sex in a generalized linear model

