10.1 Demographics

Age, height, weight, and body mass index at screening will be summarized by reporting the mean, standard deviation, median, minimum and maximum, and will be calculated by vaccine group and overall.

In addition, the frequency of age categories will be reported as 50-59, and 60-64 years (age cohort). The number and percentages of subjects by sex, country, ethnic origin, race, and previous influenza vaccine history (within the past 3 years) will be presented by vaccine group and overall.

Demographic data will be tabulated for the All-Enrolled Set, FAS Immunogenicity, PPS Immunogenicity, and Overall Safety Set.

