11.3 Secondary Objectives Analysis

Superiority of aQIV vs QIV (higher threshold) (Objective 2a)

To demonstrate that aQIV induces a superior immune response (*higher threshold*) compared to QIV in subjects 50-64 years of age as measured by HI GMT for at least one of 4 vaccine strains at 3 weeks after vaccination. aQIV will be considered to be superior to QIV if, for at least one vaccine strain at Day 22, the following statistical criteria are met:

- *Superior immune response will be demonstrated if the UL of the two-sided 98.73% CI for inter-group GMT ratio (QIV/aQIV) <0.67 for one or more vaccine strains.*

The statistical hypotheses to be tested for the secondary immunogenicity 2a correspond to:

- $H_0: GMTr_i \geq 0.67$, for all four vaccine strains at Day 22
- $H_a: GMTr_i < 0.67$, for one or more vaccine strains at Day 22

where $GMTr_i$ is the Day 22 GMT ratio of GMT_{QIV}/GMT_{aQIV} for one of the four vaccine strains.

Persistence of immune response of aQIV compared to QIV (Objective 2b)

To demonstrate greater persistence of the immune response for at least one vaccine strain at 6 months after vaccination with aQIV compared with QIV as measured by HI assay in subjects 50-64 years of age. aQIV will be considered to be superior to QIV if, for at least one vaccine strain at Day 181, the following statistical criteria are met:

- *Superior immune response will be demonstrated if the UL of the two-sided 98.73% CI for inter-group GMT ratio (QIV/aQIV) <1 for one or more vaccine strains.*

The statistical hypotheses to be tested for the secondary immunogenicity 2b correspond to:

$H_0: GMTr_i \geq 1$, for all four vaccine strains at Day 181

$H_a: GMTr_i < 1$, for one or more vaccine strains at Day 181

where $GMTr_i$ is 6-month GMT ratio of GMT_{QIV}/GMT_{aQIV} for any of the four vaccine strains.

Secondary objective analysis 2a, 2b will be carried out using the same model for GMT ratio analysis as specified for the primary objective analysis at Day 22. Endpoints at Day 22, and Day 181 for objective 2a and 2b will be tested sequentially, each at 0.0127% two-sided significance level.

To evaluate the immunogenicity of aQIV compared with QIV as measured by HI in subjects 50-64 years of age (Objective 2c)

Secondary immunogenicity endpoints 2c include the measures of immunogenicity of aQIV and QIV as determined by the HI assay against homologous strains at Day 1, Day 22, and Day 181 (unless indicated otherwise), include the following:

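### The GMT models carry no country term in a multi-country trial: the analysis is valid, but some precision is given up, chiefly for secondary objectives 2a and 2b

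*SAP*

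**What the plan says.** SAP 8.3 is a single sentence with no reason given: "There will be no adjustment for multiple centers". It says nothing about country.

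Protocol 8.4.2.3.3 fixes the covariates for the adjusted GMT ratio: treatment group, log10 prevaccination titer, and "age stratum, gender, and history of any influenza vaccination within the 3 previous influenza seasons". SAP 8.1 gives the same list for Days 22, 181 and 271, and SAP 11.2 writes out the model. Under SAP 11.3, the analysis of 2a and 2b "will be carried out using the same model for GMT ratio analysis as specified for the primary objective analysis at Day 22". None of these models has a centre or country term.

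Country is available. SAP 10.1 tabulates it as a demographic: "The number and percentages of subjects by sex, country, ethnic origin, race". More than one country is implied. Protocol 6.6 requires labelling that "complies with the legal requirements of each country where the study is to be performed", and protocol 3.10 states: "The local end of the study is defined as the Last Subject Last Visit within the country". The number and size of the countries are not given.

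The stratification factors are age group and vaccination history (protocol 5.1.4, SAP 4.1). Country is not among the subgroups in protocol 8.3.7 or SAP 8.5.

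**The concern.** HI titers can differ between countries through past exposure, past vaccination and, later in follow-up, influenza circulation. Day 1 titer and a yes/no history absorb part of this. A yes/no flag does not carry the number or type of past vaccinations, and no Day 1 covariate can carry exposure after vaccination, which may matter at Day 181. That circulation differs by country is a reasonable assumption, not a figure in the documents.

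Whatever remains goes into the residual, so the intervals for the GMT ratio are somewhat wider than a model using data already collected would give. This counts most where power is limited. Objective 2a requires the upper limit of a 98.73% interval to fall below 0.67 for at least one strain. Objective 2b is reached only through 2a (SAP 8.4 and 11.4).

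**Working it through.** **Inputs.** From SAP 5: 1,816 evaluable subjects, 908 per arm. Log10 differences (SD) are A/H1N1 0.07 (0.46), A/H3N2 0.26 (0.61) and B 0.14 (0.48). From SAP 8.4 and 11.3: threshold 0.67 and 98.73% interval for 2a. Assumed, because the documents give no value: the share r of residual variance explained by country, at 1, 2, 5 and 10%. The planning SDs are treated as residual SDs; the documents do not say whether they are crude or residual.

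**The plan's own figure.** Power = Φ(d / (SD × √(2/908)) − 1.96). For A/H1N1, 0.07 / (0.46 × 0.04693) = 3.242, and Φ(3.242 − 1.96) = 90.0%. This reproduces the stated 90%. With 10% dropout, 1,816 / 0.9 gives 2,018.

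**Objectives 1a and 1b.**
- 1b needs 2 of 4 strains. For each B lineage, 0.14 / (0.48 × 0.04693) − 1.96 = 4.25, so power exceeds 99.99%. For A/H3N2 it is 0.26 / (0.61 × 0.04693) − 1.96 = 7.12. Power for 1b is therefore about 100% whatever happens to A/H1N1.
- For GMT noninferiority, the weakest row by this measure is A/H1N1: (0.07 + log10 1.5) / 0.02159 − 1.96 = 9.44, again about 100%.
- The SCR comparison uses the Miettinen and Nurminen method without covariates, so the GMT model does not affect it.

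**Objective 2a.** The threshold on the log10 scale is −log10(0.67) = 0.1739. The planned differences for A/H1N1 (0.07) and B (0.14) lie below it, so power rests on A/H3N2, with excess 0.26 − 0.1739 = 0.0861. The critical value for 98.73% is 2.492. Power = Φ(0.0861 / (0.61 × √(1 − r) × √(2/908)) − 2.492).

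| r | Residual SD | SE | Power of 2a | Equivalent extra subjects, 1,816/(1 − r) − 1,816 |
|---|---|---|---|---|
| 0 | 0.610 | 0.0286 | 69.7% | 0 |
| 1% | 0.607 | 0.0285 | 70.2% | 18 |
| 2% | 0.604 | 0.0283 | 70.7% | 37 |
| 5% | 0.595 | 0.0279 | 72.3% | 96 |
| 10% | 0.579 | 0.0272 | 75.1% | 202 |

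**Validity.** A simulation with five countries, 4,000 trials per scenario and r of 5, 10 and 20% found the treatment estimate unbiased with and without a country term. Without the term, one-sided type I error was 0.024 to 0.026 when randomisation was not stratified by country, against a nominal 0.025.

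**Objective 2b.** The documents give no Day 181 difference, SD, attrition or country share, so no power gain is calculated.

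**The case against.** The strongest reply is that nothing is broken. The model already contains both stratification factors, sex and baseline titer. Leaving out a factor not used in randomisation is a legitimate prespecified choice, and any lost precision works against the sponsor. The size of the gain is assumed throughout: at 5% or less it is at most 2.6 points for 2a (72.3 − 69.7). All of this stands, and it limits the point to an efficiency gain.

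Several stronger readings are tempting, but the documents do not support them:

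- **Bias or an inflated error rate.** Randomisation protects the comparison, and the simulation shows neither.
- **A threat to the primary objectives because A/H1N1 is planned at only 90%.** Objective 1b needs two strains, and the other three are each at about 100%.
- **A known, larger loss at Day 181.** The mechanism is plausible, but the documents give no number for it. A country term also cannot identify which individuals were infected.
- **An explicit exclusion of country.** SAP 8.3 names centres only.
- **No possibility of results by country.** None is specified, but the table shells are a separate document (SAP 16). Protocol 8.4.2.3.3 also leaves room to examine interactions and other covariates, without naming country.

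**Conclusion.** The point holds as a minor matter of efficiency. The GMT models omit a baseline factor that is already collected, and the plan gives no reason concerning country. Objectives 1a and 1b do not depend on it. For 2a, power of about 69.7% would rise by 0.5 to 5.4 points over an assumed country share of 1 to 10%. This rests on the Day 22 planning values, on reading 0.61 as a residual SD, and on country explaining variance beyond the existing covariates. Objective 2b gains indirectly because it is reached only through 2a, and possibly directly at Day 181 by an amount that cannot be stated. If country explains almost nothing, the loss is negligible.

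**What to change.** Before unblinding, add country as a fixed factor to the GMT ANCOVA in SAP 8.1 and 11.2, with small countries pooled by a size rule set in advance. SAP 11.3 carries the model to 2a and 2b. Reword SAP 8.3 so that it addresses country as well as centre. Make the same change in protocol 8.4.2.3.3, which fixes the covariate list; editing the SAP alone would leave the two documents in conflict over the primary model.

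If the protocol model is not amended, or unblinding has occurred, keep the planned model as confirmatory. Run the country-adjusted ANCOVA at Days 22 and 181 as a sensitivity analysis labelled supportive.

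In either case, show the adjusted GMT ratio by country next to the SAP 8.5 subgroup results as a descriptive consistency display.

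The cost is a protocol and SAP wording change, one more class variable and a few degrees of freedom out of about 1,800. No new data are needed and trial conduct does not change.

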8.4 Multiple Comparisons and Multiplicity

Adjustment for multiple comparison and multiplicity is reflected in the CI of the success criteria, which kept the type I error under 5%. For secondary endpoint analyses, sequential testing and significance level adjustment will be applied to keep type I error under 5%.

For four out of four strain successes, with $\alpha=0.05$ for each strain, the overall type I error is $\alpha^4=0.00000625$.

For two out of four strain successes, with $\alpha=0.05$ for each strain, the overall type I error is $0.05^4+4 \times 0.05^3 \times 0.95+6 \times 0.05^2 \times 0.95^2=0.014019$.

For 1 out of four strain successes, with $\alpha=0.05$ for each strain, the overall type I error is $1-0.95^4=0.1855$.

Thus, for objective 1b): two out of four strain success, there is no need to adjust for $\alpha=0.05$ to keep the overall type I error under 0.05. But for objectives 2a) and 2b): 1 out of four strain success, α needs to be adjusted to 0.01274 so that the overall type I error = $1-(1-0.01274)^4=0.0499944$ which is less than 0.05. Therefore, the CI for the secondary objectives 2a and 2b have been adjusted to 98.73% to keep overall family wise error rate (FWER) under 0.05.

Confirmatory flow of tests and objectives, using a hierarchical testing approach

[figure not shown]
As soon as any success criterion is not met, confirmatory testing will stop.

PRIMARY OBJECTIVE 1a: Non-inferiority	
Tests using Antibody titer at Day 22: UL of 95% CI for GMT ratio (QIV/aQIV) for strain $i \leq 1.5$ and UL of 95% CI for SCR difference (QIV-aQIV) for strain $i \leq 10\%$, for all i , $i = 1$ to 4	Multiplicity consideration: not required, overall type I error is $< \alpha$, where $\alpha = 0.05$
	Analysis Set: PPS
Criterion: UL \leq threshold for all 8 CIs \Rightarrow Non-inferiority confirmed and continue testing	

PRIMARY OBJECTIVE 1b: Superiority for at least 2 strains - basic threshold	
Tests using Antibody titer at Day 22: UL of 95% CI for GMT ratio (QIV/aQIV) for strain $i < 1.0$, for at least 2 out of 4 strains	Multiplicity consideration: not required, overall type I error is $< \alpha$ Analysis Set: FAS
Criterion: CI UL $<$ threshold for at least 2 out of 4 strains \Rightarrow Superiority (basic threshold) confirmed and continue testing	

SECONDARY OBJECTIVE 2a: Superiority for at least 1 strain - higher threshold	
Tests using Antibody titer at Day 22: UL of 98.73% CI for GMT ratio (QIV/aQIV) for strain $i < 0.67$, for at least 1 out of 4 strains	Multiplicity consideration: α -adjusted CI Analysis Set: FAS
Criterion: CI UL $<$ threshold for at least 1 strain \Rightarrow Superiority (higher threshold) confirmed and continue testing	

SECONDARY OBJECTIVE 2b: Persistence for at least 1 strain - Day 181	
Tests using Antibody titer at Day 181: UL of 98.73% CI for GMT ratio (QIV/aQIV) for strain $i < 1.0$, for at least 1 out of 4 strains	Multiplicity consideration: α -adjusted CI Analysis Set: FAS
Criterion: CI UL $<$ threshold for at least 1 strain \Rightarrow Persistence at Day 181 confirmed and continue testing	

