A nonadjuvanted inactivated quadrivalent influenza vaccine administered as one 0.5 mL intramuscularly into the deltoid muscle. The vaccine is presented in a pre-filled needleless syringe (PFS). Each 0.5 mL dose contains 15 µg HA from each of the four influenza strains recommended by the World Health Organization for the 2021/2022 Northern Hemisphere influenza season for quadrivalent vaccines.		
Statistical Analyses:		
The primary analysis will be conducted on the immunogenicity data collected up to Day 22.		
Sample Size Estimation:		
With 1:1 randomization, a sample size of 1,816 evaluable subjects is chosen so that with one-sided alpha=0.025, there will be at least 90% power to achieve the primary objectives (1a and 1b). Assuming 10% drop out, the total sample size for the study is 2,018 subjects.		

Protocol Number: V118_23

Product Name: aQIV

Document Status: Final Version 3.0, Document Date: 11 Jul 2022

Name of Sponsor:	Protocol number:	Generic name of study vaccine(s):
Seqirus UK Limited	V118_23	MF59-adjuvanted Quadrivalent Subunit Inactivated Influenza Vaccine (aQIV) Licensed comparator: nonadjuvanted Quadrivalent Influenza Vaccine (QIV)

More details on the sample size calculation are provided in Section 8.5, Sample Size and Power Considerations of Primary Objectives.
 
aQIV will be tested against a licensed nonadjuvanted quadrivalent influenza vaccine (QIV). This study is powered to demonstrate the GMT superiority of aQIV vs QIV assessed by the four co-primary endpoints associated with primary objective 1b) at significance level of one-sided $\alpha=0.025$.
 
Hypothesis testing will be carried out by 1a) and 1b) sequentially. Only after the NI objectives are achieved, the superiority objectives will be tested. All tests are carried out with a one-sided alpha of 0.025 for each comparison. No adjustment for multiple endpoints for the primary objectives is necessary.
 
The Per Protocol Set (PPS) will be used for the noninferiority analyses, and the Full Analysis Set (FAS) will be used for superiority analyses.
 
Details on the statistical analysis can be found in Section 8, Statistical Considerations.
		

Interim Analysis: An interim analysis is not planned for this study.
		

Data Monitoring Committee: An independent Data Monitoring Committee will not be utilized for the study.
		

Schema

Table 0-1: Time and Events Schedule

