8.1.1.2 Primary Immunogenicity Endpoint(s)

Humoral immune responses in terms of HI¹³ antibody response against homologous egg-derived vaccine strains (A/H1N1, A/H2N3, B/Yamagata, and B/Victoria):

- Geometric mean titer (GMT) of HI antibodies at Day 22;
- Seroconversion rate (SCR) defined as the percentage of subjects with either a prevaccination HI titer <1:10 and a postvaccination (Day 22) HI titer $\geq 1:40$, or with either a prevaccination HI titer $\geq 1:10$ and a ≥ 4 -fold increase in postvaccination HI titer.

The derived variables are:

- GMT ratios (QIV/aQIV) at Day 22 for each strain;
- The inter-group differences in the SCRs (QIV - aQIV) at Day 22 for each strain.

To evaluate the primary immunogenicity objectives 1a and 1b, the following derived variables of GMT ratios and SCR differences will be assessed at Day 22:

1a. Noninferiority of aQIV compared to QIV will be assessed for the eight primary endpoints of HI GMT and SCR for each virus strain included in the vaccines as follows:

- The GMT ratio (QIV/aQIV) for the A/H1N1 strain;
- The GMT ratio (QIV/aQIV) for the A/H3N2 strain;
- The GMT ratio (QIV/aQIV) for the B strain (Yamagata lineage);
- The GMT ratio (QIV/aQIV) for the B strain (Victoria lineage);

¹³ In case of lack of agglutination or agglutination mediated through neuraminidase for a specific strain using HI assay, immunogenicity for that strain will be assessed as measured by microneutralization (MN) assay as an acceptable alternative.

- The difference between the SCR (QIV-aQIV) for the A/H1N1 strain;
- The difference between the SCR (QIV-aQIV) for the A/H3N2 strain;
- The difference between the SCR (QIV-aQIV) for the B strain (Yamagata lineage);
- The difference between the SCR (QIV-aQIV) for the B strain (Victoria lineage).

1b. A superior immune response of aQIV compared to QIV will be assessed for the endpoints of HI GMT for each virus strain included in the vaccines as follows:

- The GMT ratio (QIV/aQIV) for the A/H1N1 strain;
- The GMT ratio (QIV/aQIV) for the A/H3N2 strain;
- The GMT ratio (QIV/aQIV) for the B strain (Yamagata lineage);
- The GMT ratio (QIV/aQIV) for the B strain (Victoria lineage);

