8.4.2.3.1 Statistical Hypothesis

Noninferiority of aQIV to QIV (Objective 1a)

To demonstrate that vaccination with aQIV elicits an immune response that is not inferior to that of QIV containing the same virus strains among adults 50-64 years of age, aQIV will be considered to be noninferior to QIV if, for each of the four strains, the following statistical criteria are met:

- The UL of the two-sided 95% CI for the ratio of the Day 22 GMTs (GMTr) does not exceed 1.5. The GMTr will be calculated by GMT_{QIV}/GMT_{aQIV}
- The UL of the two-sided 95% CI for the difference between the SCRs does not exceed 10%. The difference in SCR will be calculated by $SCR_{QIV} - SCR_{aQIV}$

The statistical hypotheses to be tested for the primary immunogenicity objective 1a correspond to:

$H_0: GMTr_i > 1.5$, for any strain

$H_a: GMTr_i \leq 1.5$, for all strains

and

$H_0: Di > 10\%$, for any strain

$H_a: Di \leq 10\%$, for all strains

where $GMTr_i$ ($i=1,2,3,4$) is any of the 4 strain-specific Day 22 GMT ratios, namely,

- $GMTr_1=GMT_{QIV}/GMT_{aQIV}$ for A/H1N1 strain
- $GMTr_2=GMT_{QIV}/GMT_{aQIV}$ for A/H3N2 strain
- $GMTr_3=GMT_{QIV}/GMT_{aQIV}$ for B/Yamagata strain
- $GMTr_4=GMT_{QIV}/GMT_{aQIV}$ for B/Victoria strain

and D_i ($i=1,2,3,4$) is the 4 strain-specific Day 22 SCR differences ($\pi_{QIV,i} - \pi_{aQIV,i}$), namely,

- $D_1 = \pi_{QIV,1} - \pi_{aQIV,1}$ for A/H1N1 strain
- $D_2 = \pi_{QIV,2} - \pi_{aQIV,2}$ for A/H3N2 strain
- $D_3 = \pi_{QIV,3} - \pi_{aQIV,3}$ for B/Yamagata strain
- $D_4 = \pi_{QIV,4} - \pi_{aQIV,4}$ for B/Victoria strain

where $\pi_{QIV,i}$, $\pi_{aQIV,i}$ ($i=1,2,3,4$) denotes the SCRs for the 4 strains in QIV and aQIV respectively.

Superiority of aQIV to QIV (Objective 1b)

To demonstrate that aQIV induces a superior immune response compared to QIV in subjects 50-64 years of age as measured by HI GMTs at 3 weeks after vaccination for at least 2 of the 4 vaccine strains, aQIV will be considered to be superior to QIV if the following statistical criteria are met:

The UL of the 95% CI for the inter-group GMT ratio (QIV/aQIV) is <1.0 for at least 2 of the 4 vaccine strains.

The statistical hypotheses to be tested for the primary immunogenicity objective 1b correspond to:

$H_0: GMTri \geq 1$, for at least 3 of the 4 vaccine strains at Day 22

$H_a: GMTri < 1$, for at least 2 of the 4 vaccine strains at Day 22

where $GMTri$ ($i=1,2,3,4$) are defined as above.

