Hypothesis testing will be carried out by 1a) and 1b) sequentially. Only after the noninferiority objectives are achieved, the superiority objectives will be tested. Only after the primary objectives are reached, secondary objective will be tested sequentially. All primary endpoint analyses will be carried out with a one-sided alpha of 0.025 for each comparison. No adjustment for multiple endpoints for the primary objectives is necessary.

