11.4 Sequential Testing and Significance Levels

As described in section 8.4, the following test procedure will be used to keep the FWER at 2-sided 5% for primary and secondary hypotheses:

- Test hypothesis 1a) (noninferiority) and hypothesis 1b) (superiority) sequentially at 2-sided level of 5%.
- Only after the goal of hypothesis 1a) is achieved hypotheses 1b) will be tested at $\alpha=0.05$ level.

- Only after the primary goals 1a) and 1b) are achieved, the secondary hypotheses will be tested sequentially at $\alpha=0.05$ level.
- For secondary objectives, if both primary objectives are achieved, then 2a will be tested at alpha-0.01274 level (two-sided) for each strain.
- If hypothesis 2a is successful, then hypothesis 2b will be tested at alpha=0.01274 for each strain at Day 181.

The study is considered successful if the primary objective 1a (non-inferiority) is achieved.

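### SAP 8.4 gives 0.00000625 as the type I error of a four-of-four strain rule; for objective 1a, the only all-strain rule, the maximum is 0.025 one-sided, although the 1a decision rule is sound

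*SAP*

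**What the plan says.** SAP 8.4 (Multiple Comparisons and Multiplicity) works through three rules with alpha 0.05 per strain. For the first, "For four out of four strain successes", it gives alpha to the fourth power, 0.00000625. For two of four it gives 0.014019, and for one of four 0.1855. In the hierarchical flow that follows, the box for objective 1a says that no multiplicity adjustment is needed because the overall type I error is below alpha = 0.05. Its criterion is that the upper limit clears the "threshold for all 8 CIs".

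Elsewhere the plan describes 1a as follows:

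- Protocol 8.1.1.2: "Noninferiority of aQIV compared to QIV will be assessed for the eight primary endpoints", namely four GMT ratios and four seroconversion-rate (SCR) differences.
- Protocol 8.4.2.3.1 and SAP 11.2: the null holds if any one strain exceeds its margin, which is 1.5 for the GMT ratio and 10% for the SCR difference.
- Protocol 8.5: "All primary endpoint analyses will be carried out with a one-sided alpha of 0.025 for each comparison". SAP 11.4 expresses the same level as two-sided 5%.
- Protocol 8.2.1.3 and SAP 11.4: the study counts as successful if 1a is achieved.

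**The concern.** A type I error rate is the largest probability of a false claim over the whole null hypothesis. The null of 1a is a union: one inferior endpoint out of eight is enough to make the noninferiority claim false. The product 0.05 × 0.05 × 0.05 × 0.05 looks at one corner of that null, where every strain is inferior together, and it also assumes that the four tests are independent. That corner is where a false pass is least likely, so it says nothing about the maximum.

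Section 8.4 is where the SAP justifies error control, and 1a decides study success and opens the gate to every later test. If the figure were carried into a study report, it would credit that decision with an error rate the design does not have.

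**Working it through.** **Inputs.** Alpha 0.05 per strain (SAP 8.4); one-sided 0.025 per comparison (protocol 8.5); margins 1.5 and 10% (SAP 11.2). From SAP 5: 1,816 evaluable subjects at 1:1, so 908 per arm; log10 GMT differences (SD) of 0.07 (0.46) for A/H1N1, 0.26 (0.61) for A/H3N2 and 0.14 (0.48) for B; SCRs of 86% v 76%, 87% v 77% and 82% v 80%; both B lineages taken as alike.

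**Step 1: reproduce the SAP.** 0.05^4 = 0.00000625, exactly as printed. The companion figures also reproduce as binomial tails with four independent null tests at 0.05: at least two of four = 0.014019, at least one of four = 0.1855.

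**Step 2: compare the product with objective 1a.**

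| | Behind 0.00000625 | Objective 1a |
|---|---|---|
| Null | all four strains null | any strain inferior |
| Tests that must pass | 4 | 8 |
| Level in the direction of the claim | 0.05 | 0.025 |
| Dependence | independent | same subjects; GMT and SCR from the same titers |

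Even under the all-null, independent assumption the number would differ: 0.025^4 = 3.9 × 10^-7 for four one-sided tests, and 0.05^8 = 3.9 × 10^-11 for eight tests at 0.05.

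**Step 3: the bound.** If the 1a null is true, at least one endpoint j is inferior. Then P(all 8 pass) ≤ P(endpoint j passes) ≤ 0.025. This needs no independence. The bound is approached when endpoint j is at its margin and the other seven pass with probability near 1.

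**Step 4: with the plan's own figures (normal approximation).** Put the A/H1N1 GMT ratio at 1.5 and leave the other seven endpoints at design values.

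- A/H1N1 GMT: the true value is at the margin, so the pass probability is Φ(0 − 1.96) = 0.025.
- A/H3N2 GMT: SE = 0.61 × √(2/908) = 0.0286; Φ((0.1761 + 0.26)/0.0286 − 1.96) ≈ 1.
- Each B GMT: SE = 0.48 × √(2/908) = 0.0225; Φ((0.1761 + 0.14)/0.0225 − 1.96) ≈ 1.
- Each B SCR, the weakest of the rest: SE = √((0.82 × 0.18 + 0.80 × 0.20)/908) = 0.0184; Φ((0.10 + 0.02)/0.0184 − 1.96) = 0.999997.
- A/H1N1 and A/H3N2 SCR: ≈ 1.

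The product is 0.0250.

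**Step 5: correlation.** Four one-sided 0.025 tests were simulated with 1,000,000 draws per correlation.

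| Correlation | One at margin, others clearly noninferior | All four at margin |
|---|---|---|
| 0 | 0.0251 | no passes seen (expected 3.9 × 10^-7) |
| 0.5 | 0.0251 | 0.00075 |
| 0.9 | 0.0251 | 0.0094 |

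The one-at-margin result does not depend on correlation. The all-null corner depends on it heavily.

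**Step 6: GMT and SCR of one strain move together.** Assume, for illustration, normal log10 titers with SD 0.46, a pure shift between arms, seroconversion as a cut on the same scale, and a QIV SCR of 50% to 80%.

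- *SCR at its margin.* For 80% v 70% the shift is (0.8416 − 0.5244) × 0.46 = 0.146, a GMT ratio of 1.40. For 50% v 40% it is 0.2533 × 0.46 = 0.117, a ratio of 1.31. Both are inside 1.5. With the bivariate normal approximation, both tests for that strain pass with probability 0.0236 to 0.0250.
- *GMT at its margin.* The shift is 0.1761/0.46 = 0.383 SD. A QIV SCR of 80% then goes with Φ(0.8416 − 0.383) = 67.7% for aQIV, a difference of 12.3 points. That is already beyond the SCR margin, so a false pass is rarer than 0.025.

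**The case against.** The strongest reply is that nothing operative is wrong, and that stands. The 1a box says no adjustment is needed and that the error is below 0.05; both statements are true for an all-must-pass rule with unadjusted 95% intervals. No confidence level is derived from the printed figure. The sentence that draws conclusions from the three rules names only 1b, 2a and 2b, and the protocol reaches the same position on 1a without the figure.

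It is also fair that the sentence does not name 1a or noninferiority. The link is an inference from 1a being the only rule that requires every strain. And 0.05^4 is computed correctly, so the fault lies in the choice of null, not in the sum. Using two-sided 5% in one place and one-sided 2.5% in another is a matter of wording, because for an upper-limit criterion they are the same rule.

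A last objection is that 0.025 overstates the practical risk, since a strain inferior on GMT would also tend to do worse on SCR. That stands in part. It makes Step 4 a way of showing the bound and not a forecast. It does not rescue 0.00000625, because under the Step 6 assumptions an SCR endpoint at its margin brings the false-pass rate for that strain's two tests back to about 0.025.

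**Conclusion.** The stated rate is wrong as a description of 1a. The maximum type I error is 0.025 one-sided, not 0.00000625. The bound itself rests only on the union null that both documents write and on each endpoint being tested at one-sided 0.025. That it is attained rests on the other endpoints passing almost surely, as SAP 5 assumes.

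Three stronger readings are tempting, and the documents do not support them:

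- *That 1a is inflated or needs an adjustment.* It does not. Its error is held at the level the protocol declares.
- *That the design is thousands of times worse than stated.* The quotient 0.025/0.00000625 = 4,000 compares two null configurations and mixes alpha scales. It becomes 8,000 with 0.05 throughout and 64,000 with 0.025 throughout. None of these measures inflation.
- *That a bad strain would be accepted 2.5% of the time.* That is an upper bound, met only with an endpoint at its margin. A strain clearly beyond its margin would pass less often.

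This is a correction to a stated operating characteristic in a confirmatory section. It is worth making because of where the figure sits, but it does not threaten the primary conclusion.

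**What to change.** In SAP 8.4, delete the sentence with the alpha-to-the-fourth figure. In its place state that objective 1a is an intersection-union test of eight endpoints (four GMT ratios and four SCR differences), that all must pass at one-sided 0.025, and that the maximum type I error is therefore 0.025 with no adjustment needed. The 1a box can stay as it is or refer to this sentence.

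The cost is one sentence and a less favourable printed number. The two-of-four figure on the next line also assumes that all strains are null and independent. Whether that matters for 1b is a separate question that should be checked on its own, and nothing here depends on it.
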